4.3.1 Extent of Exposure

Exposure to study medication (GNX) will be summarized as the number of days on treatment, percentage of days dosed, maximum daily dose received, and total dosage received. The denominator for the percentage of days of study drug is the number of days the patient is on treatment in the respective part of the study. If the patient stops taking IP during the study, the last day that drug was taken will be used as the last day of treatment. For patients who are ongoing at the end of a specific part of the study, the last known

treatment date will be used for the last day on treatment. Exposure data will be summarized for Parts A and B of the study separately as well as overall exposure for all patients.

A listing of exposure data for each patient including total daily dose, start and end dates, and reason for any dose change will also be provided.

4.3.2 Adverse Events

Adverse events (AEs) are collected from the time of informed consent/assent through the defined follow-up period. AEs are coded using MedDRA dictionary, version 22.0 and are categorized by system organ class (SOC) and preferred term (PT). A treatment-emergent AE (TEAE) is defined as an AE that starts or worsens on or after the first day of dosing with IP. Analyses of TEAEs for Part A of the study will include AEs that start or worsen during Part A and will not include any AE that starts or worsens during Part B. For Part B of the study, TEAEs will be include events that start or worsen after the first day of Part B relative to the first day of Part B. TEAEs over the entire study will be summarized for patients who participate in both Parts A and B of the study.

Tabulations of AEs will be by patient such that an individual is only counted once per summary category. Detailed by-patient listings of all AEs reported during the study will be provided and will include verbatim and coded terms for each AE.

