k.	Concomitant AEDs or their dose must be stable for 1 month prior to screening and cannot be changed at any time prior to Visit 4, but may be adjusted during Part B.										
l.	Caregiver given seizure and medication diary and instructions for use.										
m.	During the baseline visit, the investigator and parent/caregiver/LAR will decide on a domain and identify the specific behavior that the patient exhibits that denotes the domain. This behavior will be used at subsequent visits to assess change after the initiation of IP.										
n.	Patients who discontinue IP early will be encouraged to continue with all procedures and scheduled visits.										
o.	The 4 weeks between Screening Visit and Baseline Treatment Visit can be no less than 28 days and no more than 32 days.										
p.	Only for patients who do not continue into Part B. This will occur after 2 weeks of taper and 2 weeks after completion of treatment.										
q.	Only for patients \geq 7 years old if appropriate. Otherwise clinical judgment will be used.										
r.	Only for patients that were Screened without previous genetic testing results and had a genetic test performed at the sponsor's designated lab.										

Table 1: Schedule of Assessments - Part A

WEEK	Part A										
	Screen/Baseline		Titration and Maintenance								
-4 (Screening Visit – Start of Baseline)	0 (Baseline Treatment Visit)	Day 1	Day 2	Day 3	1	2, 3, 4	5	9	12	16 Taper/Safety Visits ^p	
Visit Windows	+ 4 days			± 1 day	± 3 days	± 3 days	± 3 days	± 3 days	± 3 days	± 3 days	
VISIT	Visit 1 ^a	Visit 2 ^o	Phone Follow-up	Phone Follow-up	Phone Follow-up	Visit 3	Phone Follow-up	Visit 4	Phone Follow-up	Visit 5	Visit 5a

s. Review of medical history only.

t. Developmental examination is limited to pediatric patients 2 to 17 years of age, inclusive.

Table 2: Schedule of Assessments - Part B

Part B								
	Final Part A Visit/ First Part B Visit	Open-Label Extension (Visits will be every 8 weeks with a telephone follow-up in-between)					Final OLE Visit or Taper Visit	Safety Follow-up Post-taper
WEEK	12	16	20	24	28	32	36 or early D/C	2 weeks post last dose
Visit Windows		± 7 days	± 7 days	± 7 days	± 7 days	± 7 days	± 7 days	± 3 days
VISIT	Visit 5	Phone follow-up	Visit 6	Phone follow-up	Visit 7	Phone follow-up	Visit 8 (Week 36) ^g or Visit X (early D/C)	Visit X
Confirm patient is “OLE eligible” (≥ 35% reduction in seizure frequency)	X							
Vital signs (BP, HR, RR, and body temperature)	X		X		X		X	X

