7.3. Study Procedures (Part B: OLE Period)

7.3.1. First OLE Visit (Visit 5, Week 12)

Patients who complete Part A with a seizure reduction of \geq 35% compared to the 4-week baseline period and who do not have any other contraindications for continued treatment will continue to be treated with GNX in the OLE period (Part B) of the study. Ganaxolone patients will continue GNX treatment at the dose that they were on at the completion of Part A. The following study procedures/assessments will be completed during the final maintenance period visit in Part A (Visit 5, Week 12):

- Confirm patient OLE eligibility (\geq 35% reduction in seizure frequency)
- Vital signs (to include BP, HR, RR, and body temperature).
- Height and weight. Length will be measured if height cannot be obtained.
- Physical, neurological, and developmental examination (developmental examination is limited to pediatric patients 2 to 17 years of age, inclusive)
- ECG
- Clinical laboratory tests (chemistry and hematology)
- Urinalysis
- Drug screen (plasma) for THC and CBD
- Serum pregnancy test for all girls/women of childbearing potential
- IP Population PK sample (drawn when convenient during the visits)

- Concomitant AED review and levels if per standard of care
- [REDACTED]
- AEs
- Seizure and medication diary review
- [REDACTED]
- CGI-C (parent/caregiver/LAR identified behavioral target)
- CGI-I (parent/caregiver/LAR and clinician)
- C-SSRS (since previous visit). Only for patients \geq 7 years old if appropriate, otherwise clinical judgement will be used.
- Dispense IP

7.3.2. OLE Period and Final OLE Visit or Taper Visit (Visits 6, 7, and 8 [or Early Discontinuation], Weeks 20, 28, and 36 [or Early Discontinuation] \pm 7 days)

The following study procedures/assessments will be completed during the OLE period of the study at Visits 6, 7, and 8 (\pm 7 days):

- Vital signs (to include BP, HR, RR, and body temperature)
- Weight
- Physical, neurological, and developmental examination (developmental examination is limited to pediatric patients 2 to 17 years of age, inclusive)
- ECG (Visit 7, Week 28 and Visit 8, Week 36)
- Clinical laboratory tests (chemistry and hematology)
- Urinalysis (Visit 7, Week 28 and Visit 8, Week 36)
- Drug screen (plasma) for THC and CBD (Visit 7, Week 28)
- Serum pregnancy test for all girls/women of childbearing potential
- Tanner staging (Visit 8, Week 36)
- IP PK sample (drawn when convenient during the visits)

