4.1.5 Prior and Concomitant Medications

All investigator terms for medications recorded on the CRF will be coded using the World Health Organization Drug Dictionary Enhanced (WHODDE) Anatomical Therapeutic Chemical (ATC) drug dictionary (Version WHODDE, September 2019). The number (percentage) of subjects who took prior and concomitant medications will be summarized in the Safety population by Anatomic Therapeutic Chemical (ATC) classification level 2 and Preferred Term (PT). September 2019.

Prior medications are defined as medications that started prior to the first dose of study drug. Concomitant medications are defined as medications (other than the study drug)

taken on or after the first dose of the study drug. Medications started before the first dose of study drug and continuing at the time of the first dose of study drug are considered both prior medication and concomitant medication. The summary of concomitant medications for Part A of the study will not include concomitant medications that start after Part A; i.e., they will not include any concomitant medications starting on or after the first dosing day of the OLE phase.

The number and percentage of patients in the Safety population reporting use of prior and concomitant treatments will be summarized and listed separately. In addition, antiepileptic prior and concomitant drugs (AEDs) and rescue medications will be presented separately. Prior medications will be summarized for Part A only. All other summaries and listings will be presented separately for Parts A and B of the study.

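### SAP 4.3.2 leaves adverse events that start or worsen on the first day of Part B out of both part-specific TEAE tables, and does not define that day

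*SAP*

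**What the plan says.** SAP 4.3.2 sets three rules for treatment-emergent events.

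- General rule: a TEAE is "defined as an AE that starts or worsens on or after the first day of dosing with IP".
- Part A: the analysis covers events that start or worsen in Part A and "will not include any AE that starts or worsens during Part B".
- Part B: the analysis covers "events that start or worsen after the first day of Part B relative to the first day of Part B".

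Two further outputs do not depend on the split: "TEAEs over the entire study will be summarized for patients who participate in both Parts A and B of the study", and "Detailed by-patient listings of all AEs reported during the study will be provided".

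For concomitant medications, SAP 4.1.5 cuts at the same boundary but includes the first day on the Part B side. Of the Part A summaries it says that "they will not include any concomitant medications starting on or after the first dosing day of the OLE phase".

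SAP 4.3.2 gives no date for the first day of Part B. Other sections differ:

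- Protocol Table 2, repeated in SAP Appendix B, heads the Visit 5 column "Final Part A Visit/ First Part B Visit".
- Protocol 7.3.1 is titled as the first extension visit and names Visit 5, but its text also calls Visit 5 the last maintenance visit of Part A.
- SAP 1.2.5 runs the extension from Visit 5 to Visit 8.
- SAP 3.2, in the part on efficacy analyses, starts the extension one day after Visit 5. The same section says that safety data are not windowed.

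**The concern.** The first day of Part B lies within Part B, so the Part A rule removes an event with that onset date. It is not after the first day of Part B, so the Part B rule does not admit it. The general TEAE rule in the same paragraph and the medication rule in SAP 4.1.5 both include their boundary day. SAP 4.3.2 gives no reason for treating this boundary differently, so the wording looks like a slip.

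Preliminary safety is part of the primary objective, and long-term safety in Part B is a secondary objective. Protocol 9.7 promises summaries for Part A, for Part B and for both combined. As written, an event can be counted in the whole-study table and in neither part, so the three sets of tables need not reconcile. Because the boundary date is undefined, two programmers could also place the same event differently.

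**Working it through.** The plan states no figure to reproduce. The check applies the Part A and Part B rules literally to onset dates around Visit 5.

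**Inputs.** The Part A and Part B rules come from SAP 4.3.2. Two start dates for Part B are documented: Visit 5 (Protocol Table 2, Protocol 7.3.1, SAP 1.2.5) and Visit 5 + 1 day (SAP 3.2).

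**Rules.** Let d be the onset day relative to Visit 5 and B the first day of Part B on the same scale.

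- The event is in the Part A table if d < B.
- The event is in the Part B table if d > B (as written) or d ≥ B (with *on or after*).

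**Number of part-specific tables that hold the event**

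| Onset day | B = Visit 5, as written | B = Visit 5 + 1, as written | Either B, *on or after* |
|---|---|---|---|
| Visit 5 − 1 | 1 (Part A) | 1 (Part A) | 1 |
| Visit 5 | **0** | 1 (Part A) | 1 |
| Visit 5 + 1 | 1 (Part B) | **0** | 1 |
| Visit 5 + 2 | 1 (Part B) | 1 (Part B) | 1 |
| Visit 5 + 3 | 1 (Part B) | 1 (Part B) | 1 |

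The one-day gap exists under both start dates, and only its calendar position moves. With *on or after*, every onset day falls in exactly one table.

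**Which day is lost.** If B is Visit 5, the lost day is one on which laboratory tests, ECG, vital signs, examinations and AE review all take place. Under Protocol 8.1.5 a laboratory, vital-sign or ECG change can be an AE, and SAP 4.3.5 requires clinically significant ECG findings to be reported as AEs. Some events first detected that day could therefore carry that date. If B is Visit 5 + 1, Visit 5 events stay in Part A and the lost day has no scheduled visit.

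**Size.** The documents do not forecast how many patients enter Part B, so I assume 15 to 25. One patient is then 1/25 = 4.0% to 1/15 = 6.7% of the Part B denominator. If the event belongs in Part A instead, with about 30 treated patients (SAP 1.3.2), one patient is 1/30 = 3.3%. These are ceilings per affected patient and category. SAP 4.3.2 counts a patient once per summary category, so the count changes only if the patient has no other qualifying event in that category in that part.

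**The case against.** There are five counter-arguments.

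1. *The text can be read more kindly.* The Part A rule also includes events that start or worsen in Part A, and Visit 5 is labelled as belonging to both parts. A Visit 5 event could be said to qualify for Part A on that limb. The Part B sentence also does not say that it covers these events only. This makes the text ambiguous but does not repair it: the same sentence of the Part A rule would then both include and exclude the event.

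2. *The exclusive wording could be deliberate,* with the first day serving as the reference against which worsening in Part B is judged. Even so, events on that day need a place, and the Part A rule refuses them. Where the SAP does drop a day on purpose (the first treatment day for seizure counts, SAP 3.1.3.2), it says so and gives a reason. Here it does neither.

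3. *A reader might infer that the findings of the Visit 5 clinic assessment are what is lost.* The documents do not settle this. Most of the relevant text points to Visit 5, and the contrary period in SAP 3.2 sits under efficacy. But SAP 3.2 and the body of Protocol 7.3.1 support keeping Visit 5 in Part A. Events reported at Visit 5 with an earlier onset also stay in Part A on either reading. This objection stands.

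4. *A reader might infer that each missed event moves an incidence by 4 to 7 points.* That is a ceiling, for the reasons given with the calculation. This objection stands.

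5. *A reader might infer that safety data disappear.* They do not. Every affected patient takes part in both parts and so belongs to the whole-study summary, and the listings hold all AEs. Laboratory and ECG values are also summarised and listed separately (SAP 4.3.3 and 4.3.5).

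**Conclusion.** The one-day gap is real on the literal wording of SAP 4.3.2, whichever documented start of Part B is used. Confidence is high on that point only. It is not established that the lost day is the Visit 5 clinic day: that is the better-supported reading for safety data, but SAP 3.2 contradicts it and SAP 4.3.2 is silent.

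The consequence is a possible under-count in part-specific incidence tables, and part tables that do not reconcile with the overall table. It is limited to one calendar day per patient who continues. The 4.0 to 6.7 point ceiling rests on the assumed 15 to 25 extension patients. For an uncommon preferred term, the difference could be between zero and one patient. This is a minor point, worth correcting because the correction is nearly free.

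**What to change.** Three edits to the SAP, best made together:

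1. In SAP 4.3.2, define Part B TEAEs as those that start or worsen *on or after* the first day of Part B.
2. Define the first day of Part B once for AEs, for example as the date of the first Part B dose or as the day after Visit 5. Bring SAP 1.2.5, SAP 3.2 and the medication rule in SAP 4.1.5 into line with it, so that every onset date falls in exactly one part.
3. State explicitly to which part findings made at Visit 5 before the first Part B dose are assigned.

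The third edit matters because a bare rule that Part A ends the day before the first Part B dose could create a new problem. If that dose falls on the Visit 5 date, findings made after 12 weeks of Part A treatment would move into Part B for patients who continue, and stay in Part A for those who do not.

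The cost is two words, one definition and one sentence of assignment, plus matching edits in the sections named. Data collection does not change.

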4.3.2.1 Overview of Adverse Events

A summary of AEs reported during the study will be presented. The number and percentage of patients in the Safety Population who reported at least one occurrence of an event in one of the following categories will be summarized:

- Any TEAE
- TEAE with causality related to study drug
- Any SAE
- TEAE leading to discontinuation of study drug
- TEAEs by worst severity
- TEAEs with an outcome of death

4.3.2.2 Incidence of TEAEs

The number and percentage of patients reporting at least one TEAE during Part A, Part B and overall will be summarized by MedDRA System Organ Class (SOC) and preferred term (PT). The summary will be sorted by descending frequency within SOC and PT within SOC.

A detailed listing of AEs for each patient will be provided. The listing will include the

verbatim term reported by the Investigator, MedDRA SOC and PT, onset date/time, end date/time, severity, seriousness (yes/no), seriousness reason, relationship to study drug, action taken, withdrawal from study, treatment required, and outcome.

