3. STUDY DESIGN

3.1. Study Design and Flow Chart

This is an OL proof of concept study of adjunctive GNX treatment in patients with a confirmed clinical diagnosis of TSC and/or a mutation in either the *TSC1* or *TSC2* gene. The trial consists of two parts: Part A consists of a 4-week baseline period followed by a 12-week treatment period (4-week titration and 8-week maintenance). For patients not continuing in the OLE period (Part B), a 2-week taper period followed by a 2-week safety period would follow. The main difference between Part A and Part B is the length of treatment, less frequent assessments, and the ability to alter drug doses (both GNX and other AED treatments which includes initiating and stopping other medications) based on investigator evaluation of the patient's clinical course during Part B. Patients with a seizure frequency reduction rate of $\geq 35\%$ during the 12-week treatment period in Part A compared to baseline may continue into Part B ("OLE eligible"). If the investigator believes there is a medical benefit for the patient who does not meet the seizure reduction criterion to enter the OLE, they must discuss the patient with the sponsor medical monitor and receive sponsor approval for that patient to continue into the OLE.

Part A

- 4-week baseline period

[figure not shown]
IND 044,020
Protocol 1042-TSC-2001Marinus Pharmaceuticals, Inc.
11 Jun 2021

- 4-week titration period
- 8-week maintenance period
- 2-week taper period (For patients who do not complete Part A or after completing Part A but do not continue into Part B)
- 2-week safety follow-up visit post taper (For patients who taper off GNX)

Part B (Optional for OLE-eligible patients)

- OLE period (until the Sponsor markets ganaxolone or terminates the study)
- 2-week taper period (For patients who discontinue GNX due to early termination or completion)
- 2-week safety follow-up visit post-taper (For patients who taper off GNX)

Figure 1: Study Design

GNX = ganaxolone

During the screening visit, each patient's baseline [REDACTED] will be collected and analyzed for post-study evaluation.

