7.3.3. Telephone Follow-up (Weeks 16, 24 and 32 \pm 7 days)

A telephone follow-up visit will be conducted at Weeks 16, 24, and 32 (\pm 7 days) of the OLE period to assess the following:

- AEs
- Seizure and medication diary review

7.3.4. Safety Follow-up Post Taper (Visit X, 2 Weeks Post Last Dose \pm 3 days)

The following study procedures/assessments to be completed during the Safety Follow-up Post Taper Visit (\pm 3 days):

- Vital signs (to include BP, HR, RR, and body temperature)
- Physical, neurological, and developmental examination (developmental examination is limited to pediatric patients 2 to 17 years of age, inclusive)
- Clinical laboratory tests (chemistry and hematology)
- Urinalysis
- Serum pregnancy test for all girls/women of childbearing potential
- IP PK sample (drawn when convenient during the visits)
- Concomitant AED review and levels if standard of care
- AEs
- Seizure and medication diary review

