7.3.5. Unscheduled Visits

Unscheduled visits can occur between regularly scheduled visits. For patients who are remaining in Part B (on the OLE) after Visit 8, unscheduled visits may take place as decided by Investigator, but no longer than six months after the prior visit, or prior to exiting the study. Unscheduled Visits assessments will be conducted at the discretion of the PI. These assessments may include vital signs, laboratory testing, etc.

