9.7. Safety Analyses

Safety will be reported for all patients. The results in Part A and Part B will be summarized separately and then the combined results in Part A and Part B will be summarized together. Adverse events will be tabulated by overall, system organ class, and Preferred Term using the Medical Dictionary for Regulatory Activities (MedDRA) coding system. Incidence and percentage of AEs will be presented. Additional tables, with AEs classified by severity and by only those related to drug as assessed by the investigator will be presented. Subset listings will be produced for AEs that cause withdrawal and for SAEs. Clinical laboratory tests (hematology, chemistry and urinalysis), vital signs (temperature, BP, pulse rate), weight, and ECGs will be summarized using descriptive statistics including changes from baseline. Change in C-SSRS scores where applicable will be determined. Physical, neurological and developmental examinations will be summarized using number and percentage of patients with abnormalities.

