3.1.3.2 Post-baseline seizure frequency – Maintenance Period, Part A, Part B and Overall

Post-baseline 28-day seizure frequency will be calculated as the total number of seizures in the specified post-baseline period divided by the number of days with non-missing seizure data in the same post-baseline period, multiplied by 28. Within Part A of the study, post-baseline seizure activity will be determined based on the days following the first day after the date of the first dose of IP. The first day of treatment is included in neither the baseline nor the post-baseline period since seizures reported on that date could have occurred either before or after the initiation of treatment. Within Part B (OLE

period), post-baseline seizure activity will be determined by the first day of OLE treatment.

Separate frequencies will be calculated for the 8-week maintenance period of Part A (Maintenance), Parts A (12-week treatment period consisting of a 4-week titration period and an 8-week maintenance period) and B of the study (OLE period of up to 24 weeks) and across both study parts.

Post-baseline specified study period 28-day seizure frequency =

$$\frac{\# \text{ seizures, specified study period}}{\# \text{ specified study period days with seizure data reported}} \times 28$$

3.1.3.3 Percent change in 28-day seizure frequency – Maintenance Period, Part A, Part B and Overall

% change from baseline =

$$\frac{[(\text{post-baseline 28-day seizure frequency}) - (\text{baseline 28-day seizure frequency})]}{(\text{baseline 28-day seizure frequency})} \times 100$$

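### TEAEs are summarised only as percentages of patients over periods of unequal length; adding patient-time at overview level would let them speak to the long-term safety objective

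*SAP*

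**What the plan says.** **Measure.** SAP 4.3.2.2 reads: "The number and percentage of patients reporting at least one TEAE during Part A, Part B and overall will be summarized", broken down by SOC and PT. Under SAP 4.3.2 tabulations are by patient, so that "an individual is only counted once per summary category". The overview (4.3.2.1) and the summaries by severity, relationship and seriousness (4.3.2.3 to 4.3.2.5) are also numbers and percentages. Protocol 9.7 has the same scope: "Incidence and percentage of AEs will be presented". SAP 4.3.1 summarises days on treatment by part and overall, but no readable section links those days to adverse events.

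**Length.** SAP 3.1.3.2 describes Part A as a "12-week treatment period consisting of a 4-week titration period and an 8-week maintenance period" and Part B as an "OLE period of up to 24 weeks". Protocol 3.1 lets the OLE run until ganaxolone is marketed or the sponsor stops the study, while protocol 3.2 gives 24 further weeks. The SAP cites protocol Version 2 of 12 May 2020; the protocol supplied is dated 11 Jun 2021.

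**Contacts.** Protocol 3.1 acknowledges the contrast: "The main difference between Part A and Part B is the length of treatment, less frequent assessments". For Part B, protocol 7.3.3 says: "A telephone follow-up visit will be conducted at Weeks 16, 24, and 32", with clinic visits at Weeks 20, 28 and 36. After Visit 8, unscheduled visits are at the investigator's decision, "but no longer than six months after the prior visit, or prior to exiting the study" (protocol 7.3.5).

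**The concern.** In a fixed group of patients, a once-per-patient percentage can only stay level or rise as follow-up lengthens. A Part B or overall percentage therefore mixes how often events occur with how long patients were watched. If the OLE is open-ended, the length of watching also varies between patients.

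Long-term safety and tolerability in Part B is a secondary objective in both documents. A reader with that objective in mind will want to know how often events occur per unit of time on drug, and whether they thin out or persist. Three columns of percentages over unequal periods cannot answer that. Equal percentages in the two parts could hide a lower event rate in Part B, and a higher Part B percentage could reflect nothing but the longer period.

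**Working it through.** The documents contain no calculation to reproduce. The check counts scheduled contacts and shows how a percentage moves with time.

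**1. Scheduled post-dose AE contacts** (protocol Tables 1 and 2)
- Part A: Days 1, 2, 3 and Weeks 1, 2, 3, 4, 5, 9, 12 make 10 contacts in 12 weeks; 10/12 = 0.83 per week.
- Within Part A: 7/4 = 1.75 per week in titration and 3/8 = 0.375 per week in maintenance.
- Part B to Week 36: Weeks 16, 20, 24, 28, 32, 36 make 6 contacts in 24 weeks; 6/24 = 0.25 per week.
- Ratio of Part A to Part B: 0.83/0.25 = 3.3. Against maintenance alone it is 0.375/0.25 = 1.5, so most of the contrast comes from titration.
- Not counted: Visit 5a at Week 16 for patients who do not continue, and the post-taper visit in Part B.

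**2. Effect of length alone** (assumptions: constant hazard, equal ascertainment, and a 12-week proportion p12 that the documents do not give)

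P(t) = 1 − (1 − p12)^(t/12)

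- p12 = 30%: at 24 weeks 1 − 0.70² = 51%; at 36 weeks 1 − 0.70³ = 66%.
- p12 = 10%: 1 − 0.90² = 19%; 1 − 0.90³ = 27%.
- p12 = 50%: 1 − 0.50² = 75%; 1 − 0.50³ = 88%.

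**3. The same percentage expressed as a rate** (52.18 weeks per year)

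Rate per 100 patient-years = −ln(1 − p)/t × 52.18 × 100

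- 30% over 12 weeks: 0.3567/12 × 5218 = 155.
- 30% over 24 weeks: 0.3567/24 × 5218 = 78.

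Identical table entries would correspond to a twofold difference in rate.

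**4. Effect of sparser questioning** (assumption: Part B captures a fraction c of events)

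P(24) = 1 − (1 − p12)^(24c/12)

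- p12 = 30%, c = 0.5: 1 − 0.70 = 30%, the same as Part A.
- p12 = 30%, c = 0.3: 1 − 0.70^0.6 = 19%, below Part A.

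Length and ascertainment work in opposite directions, so the sign of a Part A to Part B difference is not determined.

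**5. Precision to expect** (assumption: 15 patients followed for the full 24 weeks of Part B)

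15 × 24/52.18 = 6.9 patient-years. Three first events give 3/6.9 = 43 per 100 patient-years, with an exact Poisson 95% CI of about 9 to 127.

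**The case against.** The strongest reply is that nothing here is wrong. The trial is single-arm and descriptive, SAP 2.1 plans no formal testing, and the two parts are tabulated separately under their own names. No section offers the Part A to Part B difference as a change in risk. Exposure is summarised, and the AE listings carry onset dates. All of this stands, and it is why the point is an improvement. It does not remove the gap. Time at risk to first event cannot be recovered from separate exposure and AE tables. The overall columns do not even match: SAP 4.3.1 gives overall exposure for all patients, while SAP 4.3.2 limits the whole-study TEAE summary to patients in both parts.

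A second reply is that one rate per patient-year summarises risk well only if the hazard is roughly constant. The documents suggest that it may not be: protocol 1.2 reports CNS events as apparently dose-related, titration fills the first four weeks, and the dosing instructions say that dizziness and tiredness usually settle within days. Nor does patient-time correct for the selection of Part B (mainly patients with at least a 35% seizure reduction) or for missed events. This stands too. It argues for splitting by interval and for a footnote.

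A third is that contact frequency is not ascertainment. AEs are collected continuously, unscheduled visits are possible, and families are told to call about side effects that interfere with daily activities. That is correct: the capture fractions in step 4 are illustrations, not estimates.

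A fourth is size. With about 30 patients, rates by SOC, PT and interval would be mostly empty cells. This stands and limits the fix to overview level.

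A reader might still infer that the percentages are invalid, that Part B will look worse than Part A, or that year-long figures should be quoted. The documents support none of these. A percentage over a named period is a legitimate description, the net direction is open, and no one-year horizon is stated.

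**Conclusion.** The plan contains no error here, but its AE summaries fall short of the long-term safety objective, and the shortfall is cheap to repair. TEAEs appear only as numbers and percentages of patients over 12 weeks, over up to 24 weeks or an open-ended period, and overall. Those percentages depend on follow-up length and cannot by themselves show how often events occur per unit of time.

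As an illustration of size, 30% at 12 weeks corresponds to 51% at 24 weeks. That rests on an assumed 12-week proportion, a constant hazard and equal ascertainment. Scheduled contacts at 0.25 against 0.83 per week pull the other way, so no net direction is claimed. The facts about measure, length and contacts come directly from the documents.

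**What to change.** Keep every planned percentage. Then:

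1. **Rates.** In SAP 4.3.2.1 (any TEAE, related TEAE, any SAE, TEAE leading to discontinuation) and for SAEs overall in 4.3.2.5, add patients with a first event per patient-year at risk, with an exact Poisson 95% CI, for Part A, Part B and overall. Count SAEs from first dose, so that events and patient-time cover the same period, and state whether taper and follow-up count as time at risk.
2. **Intervals.** At the same level, tabulate Part A by titration and maintenance, and Part B by Weeks 12-24, 24-36 and after 36 where the OLE continues. Give number at risk and patient-years for each, because the hazard may be higher during titration. Set the titration boundary by study day: SAP 3.2 ends titration at Visit 4 and labels it Day 28, while the schedule puts Visit 4 at Week 5.
3. **Limit.** Do not extend the rates to every SOC/PT cell.
4. **Footnote.** State that contact frequency differs between the parts, that Part B is mainly patients with at least a 35% seizure reduction, that the overall summary covers only patients in both parts, and that patient-time corrects none of these.
5. **Reconcile** the SAP's 24-week OLE with the open-ended OLE in protocol 3.1.

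The cost is SAP wording and a few extra tables from data already collected. The downside is wide intervals.
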